| ENDPOINTS | 
 1. Diagnostic: 
 a. Concordance of 68Ga-PSMA PET and Nano MRL |

| | |
|----------------------|---|
| | 
 b. Histology of LND c. Concordance of (a) and (b) d. Results of reimaging after LND 
2. Clinical – Follow up at 24 months
 |
| STATISTICAL ANALYSES | We will recruit 120 patients. Considering that each patient has 6 packets (a lump of fat containing lymph nodes) on average, we will be comparing 720 packets in total. This number will give 90% power to detect a 10% or less discordance between final histology analysis and the combined imaging modalities consensus. |
| STUDY DURATION | 10 years (Anticipated January 2016 to December 2026) |

CONTENTS

| | |
|--|-----------|
| 1. BACKGROUND | 9 |
| 1.1. DISEASE BACKGROUND | 9 |
| 1.2. RATIONALE FOR PERFORMING THE STUDY | 11 |
| 2. STUDY OBJECTIVES | 12 |
| 2.1. PRIMARY OBJECTIVE | 12 |
| 2.2. SECONDARY OBJECTIVES | 12 |
| 3. STUDY DESIGN | 12 |
| 3.1. DESIGN | 12 |
| 3.2. STUDY GROUPS | 12 |
| 3.3. NUMBER OF PARTICIPANTS | 12 |
| 3.4. NUMBER OF CENTRES | 13 |
| 3.5. DURATION | 13 |
| 4. PARTICIPANT SECTION | 13 |
| 4.1. INCLUSION CRITERIA | 13 |
| 4.2. EXCLUSION CRITERIA | 13 |
| 5. STUDY OUTLINE | 14 |
| 5.1. STUDY FLOW CHART | 14 |
| 5.2. INVESTIGATION PLAN | 15 |
| 5.3. STUDY PROCEDURE RISKS | 17 |
| 5.4. RECRUITMENT AND SCREENING | 18 |
| 5.5. INFORMED CONSENT PROCESS | 18 |
| 5.6. ENROLMENT PROCEDURE | 18 |
| 6. SAFETY | 18 |
| 6.1. ADVERSE EVENT REPORTING | 18 |
| 6.2. SERIOUS ADVERSE EVENT REPORTING | 18 |
| 6.3. DATA SAFETY AND MONITORING BOARD | 19 |
| 6.4. EARLY TERMINATION | 19 |
| 7. STATISTICAL CONSIDERATIONS | 19 |
| 8. CONFIDENTIALITY AND STORAGE AND ARCHIVING OF STUDY DOCUMENTS | 21 |
| 9. FUNDING | 22 |
| 10. OTHER STUDY DOCUMENTS | 22 |
| 11. REFERENCES | 33 |

1.BACKGROUND

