7. STATISTICAL CONSIDERATIONS

a) Trial Size:

We will now recruit 120 patients (60 from St Vincent’s Hospital, Sydney and 60 from the Wesley Hospital, Brisbane) from the originally planned 80 patients. Based on the previous calculation, that each of the 80 patients will have 6 packets (a lump of fat containing lymph nodes) on average, we will be comparing 480 packets in total. This number will give 90% power to detect a 10% or less discordance between final histology analysis and the combined imaging modalities consensus. Sample size was calculated based on agreement of combination of both images together with histology. We used 15% as the probability of positive lymph node from histology results, based on literature the probability of positive lymph node result from histology is between 11% and 17% [35].

For 95% sensitivity and 90% specificity of combination of the two images, we need to test 178 packets. To achieve this number of packets we need to recruit a maximum of 32 patients. To account for correlation between packets from each patient, we have considered high effect size of equal to 2.5 which results in the requirement of 80 patients. The new recruitment target will exceed this requirement.

Statistical calculations for the MAGNIFI trial sample size are set out below:

The data for N patients, with n packets per patient, will be tabulated as follows:

| Combined Test | Histology | | Total |
|---------------|-----------|----------|-------|
| | Positive | Negative | |
| Positive | A | B | A+B |

| | | | |
|----------|-----|-----|-----|
| Negative | C | D | C+D |
| Total | A+C | B+D | N×n |

To take account of clustering, a variance inflation factor VIF is calculated as follows:

$$VIF = 1 + (n-1)\rho$$

where n is the number of packets per patient (6) and ρ is the intra-class correlation, a measure of clustering within patients (assumed to be a maximum of 0.3). This yields a VIF of 2.5.

The formula for the sample size for a two sided McNemar test, taking into account the VIF, is then (based on reversing equation (5) of Gönen, 2004):

$$N = \frac{(z_{1-\alpha/2}\phi + z_{1-\beta}\sqrt{\phi^2 - 0.25\delta^2(\phi + 3)})^2}{n\phi\delta^2/(1 + (n\phi - 1)\rho)}$$

where:

z is a percentile from the standard normal distribution

α is the level of significance (two-sided test, α = 0.05)

1-β is the power (assumed to be 0.90)

φ is the total proportion of discordant pairs: (B+C)/ (N×n) in above table

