δ is the difference in the proportions of the two types of discordant pairs: (B-C)/ (N×n)

n = number of observations per patient (6)

For the calculations, it was additionally assumed that the proportion of positive packets was 0.15, φ = 0.10, and δ = 0.04. This assumes the following proportions:

[figure not shown]
| Combined Test | Histology | | Total |
|---------------|-----------|----------|-----------|
| | Positive | Negative | |
| Positive | 0.12 | 0.07 | 0.19 |
| Negative | 0.03 | 0.78 | 0.81 |
| Total | 0.15 | 0.85 | N×n = 480 |

Gonen M. Sample size and power for McNemar's test with clustered data. *Statistics in Medicine* 2004, 23: 2283-2294

b) Statistical Analysis:

We will compare 'packet concordance rate' between histology and MR Lymphography using a MRA arterial map (that can be acquired at the MRL) to locate the position of the lymph node, the 68Ga PSMA PET SCAN plus a combined evaluation, and histology. As indicated in the diagram below, lymph nodes are removed by one lump of fat (region-packet) at a time (refer to region-packets 'a' to 'f' in figure below). The two tests (MR lymphography and 68Ga PSMA PET) will indicate (with error)

whether each node is positive or not, and thus whether each region-packet is positive (at least one node positive) or not (no nodes positive). The combined evaluation is a consensus of the two tests: region-packets are positive if one or both tests indicate positive and negative only if both tests indicate the region-packet is negative. Using histology, we can assess the accuracy of the two tests (plus combined evaluation) in terms of false positives.

| | Histology | MR Lymphography | Ga68 PSMA | Imaging Consensus |
|---|-----------|-----------------|-----------|-------------------|
| a | Negative | Negative | Negative | Negative |
| b | Positive | Positive | Positive | Positive |
| c | Negative | Positive | Positive | Positive |
| d | Negative | Negative | Negative | Negative |
| e | Positive | Positive | Positive | Positive |
| f | Positive | Negative | Negative | Negative |

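### The stated 90% power does not follow from the protocol's own inputs: 80 patients give 41% to 86%, and 120 give 58% at the clustering allowance that the protocol states.

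*Protocol*

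**What the plan says.** Section 7a gives two routes to a sample size.

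- The first starts from accuracy: "For 95% sensitivity and 90% specificity of combination of the two images, we need to test 178 packets". It turns these packets into at most 32 patients and then inflates: "we have considered high effect size of equal to 2.5 which results in the requirement of 80 patients". It adds, of the increase to 120 patients, "The new recruitment target will exceed this requirement".
- The second is a formula for a McNemar test with clustered data. Its inputs are "α is the level of significance (two-sided test, α = 0.05", "1-β is the power (assumed to be 0.90", six packets per patient, and ρ with a stated maximum of 0.3. The VIF is given as 1 + (n−1)ρ = 2.5. For the rest, "it was additionally assumed that the proportion of positive packets was 0.15, φ = 0.10, and δ = 0.04". A planning table with total N×n = 480 sets out the assumed proportions.

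On power, section 7a says of 480 packets, and the synopsis of 720: "This number will give 90% power to detect a 10% or less discordance between final histology analysis and the combined imaging modalities consensus".

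**The concern.** The 80 patients and the 90% power should both come out of the formula and inputs printed beside them, and they do not. The 80 comes from the accuracy route, while the formula and the planning table describe a different scenario. The formula is introduced as allowing for the VIF, but its denominator carries 1 + (nφ−1)ρ, which is not the VIF defined just above it.

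This is the trial's only sample-size justification. If the clustering is near what the protocol says it allowed for, 120 patients fall well short of 90%. A reader of the results would then credit the comparison of imaging with histology with more power than it had.

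**Working it through.** **Inputs, all from section 7a.** φ = 0.07 + 0.03 = 0.10; δ = 0.07 − 0.03 = 0.04; z for two-sided α = 0.05 is 1.960; z for 90% power is 1.2816; n = 6; ρ = 0.3 at most.

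**The plan's own figure.** 32 patients × 2.5 = 80 patients, and 80 × 6 = 480 packets. So the 80 is the accuracy route multiplied by the VIF; it is not an output of the formula.

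**Packets before clustering, from the printed formula.**

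- √(φ² − 0.25δ²(φ+3)) = √(0.01 − 0.25 × 0.0016 × 3.1) = √0.00876 = 0.0936
- Numerator: (1.960 × 0.10 + 1.2816 × 0.0936)² = 0.3159² = 0.0998
- Divided by φδ² = 0.10 × 0.0016 = 0.00016: 623.9 packets, and 623.9 / 6 = 104 patients

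**Clustering factor.**

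- As printed in the denominator: 1 + (6 × 0.10 − 1) × 0.3 = 0.88
- As defined in the text: 1 + (6 − 1) × 0.3 = 2.5

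**Patients needed, and power at 80 and 120.** Solve the same formula for power, with effective packets m = 6N / factor: power = Φ[(√(mφδ²) − 1.960φ) / 0.0936].

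| Clustering factor | Patients for 90% | Power at 80 | Power at 120 |
|---|---|---|---|
| 0.88 (printed term) | 623.9 × 0.88 / 6 = 91.5, so 92 | 86% | 96% |
| 1 (no clustering) | 104 | 81% | 94% |
| 2.5 (stated VIF) | 623.9 × 2.5 / 6 = 259.9, so 260 | 41% | 58% |

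For 480 packets to give 90%, the factor would have to be 480 / 623.9 = 0.77, lower than even the printed term.

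Two other standard McNemar formulas give 272 and 274 patients in the last row. A simulation with a within-patient correlation of 0.3 in the signed discordance gave about 43%, 59% and 89% power at 80, 120 and 260 patients.

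**Power at 120 patients for smaller ρ, with the stated VIF formula.**

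| ρ | VIF | Power at 120 |
|---|---|---|
| 0.3 | 2.5 | 58% |
| 0.2 | 2.0 | 68% |
| 0.1 | 1.5 | 81% |
| 0.05 | 1.25 | 87% |
| about 0.03 | 1.15 | 90% |

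The last row follows from 720 / 623.9 = 1.15, the largest factor at which 720 packets still give 90%.

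**The two scenarios.** The planning table implies a sensitivity of 0.12 / 0.15 = 80% and a specificity of 0.78 / 0.85 = 92%. The accuracy route assumes 95% and 90%.

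**The case against.** The strongest reply is that the protocol never computes the combination that gives 260 patients. It applies 2.5 to the 178-packet base, and it pairs φ and δ with a formula whose clustering term is 0.88. Taken literally, that formula needs 92 patients, and 120 give 96%. This stands in part: the shortfall at 120 depends on using the stated VIF. But a factor below 1 with positive ρ treats clustering as a gain in information, and it contradicts the 2.5 that the formula is said to take into account. The printed term therefore cannot support the claim.

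The 2.5 is also a ceiling. A reader might infer that the trial simply has 58% power or needs 260 patients. The text does not support that, because ρ is given only as a maximum and the protocol does not say what it measures: node positivity, discordance or the direction of discordance. If clustering acted only among discordant packets, a factor of 1 + (n−1)φρ = 1.15 would be arguable, and 120 patients would then give 90%. The simulation does not settle this, since it assumes one meaning of ρ.

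Four other stronger readings should not be pressed.

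- *480 packets miss 90% on every reading.* δ is printed to two decimals. With δ = 0.043 and the 0.88 term, 80 patients give just over 90%. Whether the 80 arose that way cannot be known. The same rounding does not rescue 120 patients at VIF 2.5, where power is about 65%.
- *178 packets and 32 patients are themselves errors.* The protocol does not say which method gave 178, and 32 is described as a maximum.
- *The same 90% at 480 and at 720 packets is a separate error.* Section 7a ascribes the 480 to the previous calculation for 80 patients. Carrying the figure into the synopsis is loose wording.
- *A null result would be no better than a coin toss.* Section 7b plans accuracy measures and hierarchical modelling and names no McNemar test.

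**Conclusion.** The point holds. On the inputs as printed, 80 patients give 81%, 86% or 41% power, depending on the clustering factor, and never 90%. The current 120 patients give 94%, 96% or 58%, so the synopsis claim fails at the clustering allowance that the protocol itself states. It is met only if the factor is about 1.15 or less, which under the protocol's VIF formula means ρ of about 0.03, a tenth of the stated maximum.

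Two contradictions hold whatever ρ turns out to be: 0.88 against 2.5 for the clustering factor, and 95%/90% against an implied 80%/92% for sensitivity and specificity.

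These figures assume exactly six usable packets per patient, φ and δ exactly as printed, and the McNemar formula as the basis for power. No allowance was made for incomplete packets.

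**What to change.** In section 7a and the synopsis:

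1. State what ρ measures and which value or range is assumed.
2. Use one scenario and one clustering factor, at least 1, and put that factor into the formula in place of 1 + (nφ−1)ρ.
3. Make the planning table agree with the stated sensitivity and specificity.
4. Remove the derivation from 178 packets through 32 to 80 patients, and the sentence that the new target exceeds the requirement.
5. Replace the 90% statement with the power at 120 patients and its range: about 58% at the maximum VIF of 2.5, 81% at ρ = 0.1, and 90% only if the factor is about 1.15 or less. If the choices in steps 1 to 3 change φ or δ, recompute these figures.

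The cost is protocol wording only. No extra patients are asked for; the stated power becomes less favourable.

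### Section 7a declares a VIF of 2.5 but prints a clustering term worth 0.88; at its McNemar inputs 80 men do not reach 90% power, and 120 men reach it only if the correlation is about 0.03 or less

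*Protocol*

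**What the plan says.** Section 7a sets VIF = 1 + (n − 1)ρ with n = 6 packets per man and ρ, a measure of clustering within patients, assumed to be at most 0.3. It concludes: "This yields a VIF of 2.5". It continues: "The formula for the sample size for a two sided McNemar test, taking into account the VIF, is then", and prints a formula whose clustering term is 1 + (nφ − 1)ρ. The inputs are a two-sided α of 0.05, power 0.90, φ = 0.10 and δ = 0.04; for prevalence, "it was additionally assumed that the proportion of positive packets was 0.15". The table of assumed proportions that follows carries a total of 480 packets.

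Earlier in 7a a different calculation appears. For 95% sensitivity and 90% specificity of the combined imaging, 178 packets are needed, put at no more than 32 patients; a factor of 2.5 then gives 80 patients. Of the increase to 120 the section says: "The new recruitment target will exceed this requirement".

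The power claim, "This number will give 90% power to detect a 10% or less discordance", is attached to 480 packets in section 7a and to 720 packets in the synopsis.

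**The concern.** A term that is meant to inflate the sample for clustering should exceed 1 when the correlation is positive and should grow with it. The printed term does the opposite whenever nφ is below 1, and here nφ = 6 × 0.10 = 0.6. The text and the formula therefore describe two different adjustments, one of 2.5 and one of 0.88.

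This is the only power the protocol states. If it does not follow from the plan's formula or from its declared factor, readers will misjudge what the packet-level comparison with histology can detect.

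**Working it through.** **Inputs (section 7a).** n = 6, ρ = 0.3 (stated maximum), φ = 0.10, δ = 0.04, two-sided α = 0.05 (z = 1.960), power 0.90 (z = 1.282).

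**Clustering factor F.**
- Declared: 1 + (6 − 1) × 0.3 = 2.5.
- Printed in the formula: 1 + (6 × 0.10 − 1) × 0.3 = 0.88.

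**Required number of men.** N = F × [z₁₋α/₂ φ + z₁₋β √(φ² − 0.25δ²(φ + 3))]² / (nφδ²).
- Square root: √(0.01 − 0.25 × 0.0016 × 3.1) = √0.00876 = 0.0936.
- Numerator: (0.1960 + 1.282 × 0.0936)² = 0.0998.
- Unclustered packets: 0.0998 / (0.10 × 0.0016) = 624, or 104 men.
- Printed term: 104 × 0.88 = 91.5, so 92 men.
- Declared VIF: 104 × 2.5 = 260 men.

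The formula does not reproduce 80. It also moves the wrong way: 104 men at ρ = 0, 92 at ρ = 0.3, and 67 at ρ = 0.9 (104 × 0.64).

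**Power at the planned sizes.** Inverting the formula, power = Φ{[√(Nnφδ²/F) − 1.960φ] / 0.0936}.

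| Clustering factor | 80 men (480 packets) | 120 men (720 packets) |
|---|---|---|
| 0.88, as printed | 86% | 96% |
| 1, ρ = 0 | 81% | 94% |
| 1.5, ρ = 0.1 | 63% | 81% |
| 2.0, ρ = 0.2 | 50% | 68% |
| 2.5, ρ = 0.3 | 41% | 58% |

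Example, 120 men at 2.5: 720/2.5 = 288 effective packets; √(288 × 0.00016) = 0.2147; (0.2147 − 0.1960)/0.0936 = 0.20; Φ = 0.58.

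For 90% power at 120 men the factor may be at most 720/624 = 1.154, so ρ may be at most 0.154/5, about 0.03.

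**Checks at factor 2.5.** The usual unconditional McNemar formula gives 272 men for 90% power, and power of 42% at 80 men and 58% at 120. A simulation of a cluster-adjusted McNemar test with ICC 0.3 (10,000 runs) gave 42% and 59%.

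**Where 80 comes from.** 32 × 2.5 = 80, by the sensitivity and specificity route. (178/6 is 29.7, so 32 already includes some unexplained allowance; 178 × 2.5/6 would give 75.) That route does not share the McNemar inputs:
- The McNemar table implies sensitivity 0.12/0.15 = 80% and specificity 0.78/0.85 = 92%.
- 95% and 90% at prevalence 0.15 imply φ = 0.15 × 0.05 + 0.85 × 0.10 = 0.0925 and δ = 0.085 − 0.0075 = 0.0775.

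Putting φ = 0.0925 and δ = 0.0775 into the same formula with VIF 2.5 gives 52 men for 90% power, and about 99% power at 80 men.

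**The case against.** **The 80 already carries the 2.5.** This is right. A reader might infer that the 0.88 term produced the target, or that nothing in the protocol yields 80. Neither is supported: section 7a shows 32 × 2.5. What fails is the attachment of 90% power to 480 packets by the McNemar calculation that the section then sets out.

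**The low figures depend on the input set.** Also right. Under 95% and 90% accuracy, 80 men would have ample power. But 7a ties φ = 0.10 and δ = 0.04 to its sample-size calculations and prints a table with 480 packets. The two input sets conflict and the document does not choose between them.

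**ρ may mean something else, and 0.3 is a ceiling.** If ρ were the correlation among discordant pairs only, the factor could be 1 + (n − 1)φρ = 1.15. If ρ described histology alone, with imaging errors independent given histology (an assumption, not in the protocol), the contrast's ICC would be (0.03/0.15 + 0.07/0.85)² × 0.3 × 0.15 × 0.85 / (0.10 − 0.04²) = 0.031, a factor of about 1.155. Either gives about 75% at 80 men and 90% at 120. So 58% is not the only possible answer, and the simulation does not settle this because it builds in the 2.5 reading. Yet the protocol declares 2.5, and neither alternative produces a factor below 1 or rescues 480 packets.

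**The two 90% statements.** A reader might infer that 90% for both 480 and 720 packets is a flat contradiction. Section 7a labels 480 as the previous calculation, and the synopsis figure can be read as a carried-over floor. The difficulty is that the floor itself is not established.

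**Consequences.** The protocol nowhere says that a non-significant McNemar test will be taken as agreement, and it also plans accuracy measures and hierarchical modelling. The harm is a misleading power statement, not a documented misuse of the test.

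**Conclusion.** The point holds as an error in the printed sample-size justification. The declared factor (2.5) and the formula's clustering term (0.88) contradict each other, and the latter cannot be a variance inflation under positive correlation. At φ = 0.10 and δ = 0.04, 90% power at 80 men fails on every reading of the clustering examined; the most favourable, the formula as printed, gives 86%. At 120 men power is 94% at ρ = 0 and 58% at the assumed maximum, and is 90% or more only for ρ up to about 0.03. The statement that 120 exceeds the requirement does not hold for the McNemar inputs at VIF 2.5, where 260 men are needed.

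These figures rest on the McNemar inputs and on ρ entering through the VIF that the protocol defines. They do not show that the trial's power is 58%, nor that enrolment must rise to 260: 0.3 is a ceiling, and the 95%/90% inputs would give a far more favourable answer.

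**What to change.** In section 7a:
- Make the clustering term in the formula agree with the declared VIF, or define ρ explicitly in another way and restate the VIF to match.
- Choose one set of accuracy inputs, and make the sensitivity, specificity, φ, δ and table of proportions consistent with it.
- Replace the 90% for 480 packets with the power at 120 men (720 packets) over ρ from 0 to 0.3. If φ = 0.10 and δ = 0.04 are kept, this is 94%, 81%, 68% and 58% at ρ = 0, 0.1, 0.2 and 0.3.
- Withdraw the sentence that the new target exceeds the requirement, or limit it to the inputs for which it is true.

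In the synopsis, replace the 90% for 720 packets with the same range.

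The cost is protocol wording and a less favourable stated power. Enrolment and procedures need not change.

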| | 
 • Previous surgery in pelvis (e.g. bilateral hip replacement) that limit the extent of pelvic lymph node dissection • Patients who refuse radical prostatectomy or pelvic lymph node dissection • Patients who refuse to join the trial or are unable to consent • Patients not being considered for further therapy • Patient has absolute contra-indications to undergoing MRI scanning • Patients who cannot lie still for at least 60 to 75 minutes or comply with imaging • Subject has medical conditions that would limit study participation (per physician discretion) • Subject is enrolled in one or more concurrent studies that would confound the study results of this study as determined by the study investigators • Subject has a limited life expectancy that would not allow completion of the 24 month visits |
| STUDY PROCEDURES St Vincent's Hospital, Sydney | 
 1. Men diagnosed with prostate cancer are referred to a participating urologist for a radical prostatectomy 2. The patients are consented to the study by the urologist following fulfilment of the selection criteria 3. The patient is referred to the Department of Nuclear Medicine, St Vincent's Hospital, Sydney 4. The 68Ga-PSMA PET Scan is performed at the Department of Nuclear Medicine, St Vincent's Hospital, Sydney 5. On the return visit, "Combidex" is administered to the patient and the patient is referred to Medscan Barangaroo for a MRI scan 6. Radiologist and Urologist annotate suspect lymph nodes using the Pelvic Lymph Node Diagnostic Template and assign index of suspicion to each area 7. Patient undergoes radical prostatectomy including the removal of lymph nodes 7-10 days following Combidex nano-MRL 8. The prostate and the lymph nodes are sent to histology for reporting 9. Analysis: 
 a. Histology Vs Nano-MRL b. Histology Vs Ga68 PSMA PET c. Histology Vs Nano-MRL Vs Ga68 PSMA PET 10. Repeat Ga68 PSMA and Nano-MRL if not concordant with Histology within 6-8 weeks of surgery 11. Follow up Visits: The participant will have clinical follow up reviews as part of their care at 6 weeks, 2 months, 6 months, 12 months and 24 months 12. Participant will complete the Expanded Prostate Cancer Index Composite (EPIC) survey at baseline (prior to surgery), 6 weeks, 3 months, 6 months, 1 years and then yearly for a minimum of 5 years). |

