3.5. DURATION

This study is anticipated to run for 10 years. The first two years will be dedicated for participant recruitment while the subsequent years will be dedicated for participant follow-up and the completion of the Expanded Prostate Cancer Index Composite (EPIC Survey).

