After dissection, the specimens will be sent to pathology for histopathological examination. The lymph nodes will be reviewed at 2mm dissections. The result of histological examination of the lymph nodes (gold standard) will be compared with the result of 68Ga-PSMA PET scan and Nano MRL. Sensitivity, specificity, positive predictive value (PPV), and negative predictive value (NPV) for Nano MRL and Ga68-PSMA PET scan in pelvic lymph nodes with corresponding CT size measurement in comparison with histopathology will be assessed for detection of lymph node metastases.

Analysis will include assessing sensitivity, specificity, diagnostic accuracy, positive and negative predictive values for different levels of Nano MRL and PSMA PET avidity in pelvic lymph nodes with corresponding CT size measurement in comparison with histopathology.

5. *Re-imaging*

In participants where the 68Ga-PSMA PET and/or Nano MRL detected metastases in the lymph nodes but these were not seen in the histopathology (i.e., a false positive result), the participant will undergo a repeat PSA test, a 68Ga PSMA PET scan and a Nano MRL 6 weeks after the radical prostatectomy to confirm the accuracy of the original results and to ensure that no other sites of metastases missed. As noted in section 5.3, correspondence from [name] (Appendix D) and from clinical evidence to date, there have been no safety issues as a consequence of having a repeat 68Ga PSMA PET scan and/or a Nano MRL. All precautionary safety measures will be performed.

6. Follow up visits

As part of the participant's clinical care, follow up consultations with the treating urologist are planned for 6 weeks, 2 months, 6 months, 12 months and 24 months post surgery.

7. Quality of Life (QOL) survey

To determine the outcome of treatment, the participant will be asked to complete the self-reporting Expanded Prostate Cancer Index Composite (EPIC) survey. The EPIC survey has been extensively used to report on the physical, emotional and psychological outcomes of the prostate cancer patients. The participant will ask to complete the survey at baseline (prior to surgery), at 6 weeks, 3 months, 6 months, 1 year and then yearly for a minimum of 5 years.

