We will calculate the CONCORDANCE rate for positive nodes in each packet with their corresponding region on imaging, both against each individual imaging modality and against a summed score from both imaging techniques. Sensitivity, specificity, negative predictive values (NPVs), and positive predictive values (PPVs) will be reported [31, 32]. The maximum likelihood estimates (MLEs) of PPV and NPV will be calculated from the MLEs of the sensitivity, specificity, and prevalence rate. Hierarchical modelling will be used to test for concordance between matched results from each packet.

Secondary outcome of interest is quality of life and the complications. As part of initial longitudinal analyses quality of life (as measured using EORTC-QLQ-C30) will be evaluated using one-way ANOVA. To examine differences in quality of life scores between the two groups (standard eLND versus super-eLND), baseline characteristics will be compared between groups to assess whether the groups are balanced using Chi-square tests and Fisher's exact tests. The additional analysis involves comparing the change in quality of life scores (worsened, stable or improved quality of life) from baseline to 2 and 6 months between the groups using Chi-square tests and Fisher's exact tests. Similar method will be used evaluating the differences in the complication score.

c) Interim Analysis:

An analysis of the data will be performed after every 10 patients have completed imaging and pelvic lymph node dissection. This will allow the trial statistician and data monitoring committee to identify any problems or discrepancies with data collection and recording, in addition to identifying any possible technical issues that might jeopardise

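### Section 7b analyses quality of life with the QLQ-C30 at 2 and 6 months, but the only questionnaire scheduled is EPIC, and none is due at 2 months

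*Protocol*

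**What the plan says.** **The analysis.** Protocol section 7b makes quality of life, together with complications, a secondary outcome. It states that "quality of life (as measured using EORTC-QLQ-C30) will be evaluated using one-way ANOVA" as part of initial longitudinal analyses. An additional analysis classes each man as worsened, stable or improved "from baseline to 2 and 6 months between the groups", using chi-square and Fisher's exact tests. The groups are standard eLND and super-eLND.

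**The data collection.** Section 5.2, item 7 (the quality-of-life survey) says that "the participant will be asked to complete the self-reporting Expanded Prostate Cancer Index Composite (EPIC) survey", and gives the times as "at baseline (prior to surgery), at 6 weeks, 3 months, 6 months, 1 year and then yearly for a minimum of 5 years". Item 12 of the synopsis procedures agrees: "Participant will complete the Expanded Prostate Cancer Index Composite (EPIC) survey at baseline", followed by the same times. Section 3.5 also names EPIC alone as the survey that fills the years after recruitment.

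**The visits.** Synopsis item 11 and section 5.2, item 6 plan clinic reviews at 6 weeks and at 2, 6, 12 and 24 months. Neither attaches a questionnaire to these reviews.

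**The design.** Section 3.2 says that there is one study group.

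**The concern.** The analysis section and the collection sections describe different things. One names an instrument that no visible procedure administers, and a time at which no survey is due. The others schedule a different instrument on a different calendar. An analyst who follows section 7b literally would have no scheduled scores to analyse. One who uses EPIC would be departing from the protocol's stated outcome measure, and would have to decide without guidance what takes the place of the 2-month point.

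This is not a detail left open for a later analysis plan. The protocol fixes the instrument and the times, and fixes them inconsistently with its own schedule. The conflict is in current text, and the synopsis agrees with section 5.2, so section 7b is the outlier.

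At stake is the secondary quality-of-life result. The diagnostic comparison of imaging with histology does not depend on it.

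**Working it through.** No sample size, power or error rate enters this point. The check sets the analysis against the collection schedule.

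| | Analysis (section 7b) | Collection (synopsis item 12; section 5.2, item 7) | In common |
|---|---|---|---|
| Instrument | EORTC QLQ-C30 | EPIC | none |
| Times | baseline, 2 months, 6 months | baseline, 6 weeks, 3, 6 and 12 months, then yearly for at least 5 years | baseline, 6 months |
| Groups | standard eLND, super-eLND | one study group (section 3.2) | contrast not defined |

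**Step 1, instrument.** The QLQ-C30 appears in section 7b and nowhere else in the visible text. EPIC is named in the synopsis, section 3.5 and section 5.2, but not in section 7b.

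**Step 2, times.** Two change comparisons are planned.
- Baseline to 2 months: no survey is scheduled at 2 months. Two months is 2 × 52/12 = 8.7 weeks. The nearest surveys are at 6 weeks (2.7 weeks earlier) and at 3 months, or 13 weeks (4.3 weeks later). Nothing in section 7b says which would serve.
- Baseline to 6 months: EPIC is scheduled at both ends.

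**Step 3, count of usable comparisons.**
- As written (QLQ-C30): 0 of 2 have scheduled data.
- With EPIC substituted and the times left alone: 1 of 2 (baseline to 6 months).
- With EPIC substituted and 2 months moved to a scheduled time such as 3 months: 2 of 2.

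**Step 4, groups.** Even with instrument and times corrected, the tests compare two groups that the design does not set up. Section 5.2, item 3 describes extended dissection for all men, with suspicious nodes on imaging additionally targeted, and with nodes outside the template possibly resected at the surgeons' discretion. No visible text says at what point a dissection becomes super-eLND. The comparison of complication scores, which section 7b says will use a similar method, needs the same definition.

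**The case against.** The strongest reply is that little hangs on this. Quality of life is in neither stated objective, is not in the synopsis endpoint list (diagnostic endpoints and clinical follow-up at 24 months), and plays no part in the sample size. It is called a secondary outcome only in section 7b. That stands, and it limits the severity.

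Several stronger readings are tempting, and the document does not support them.

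- *The quality-of-life analysis cannot be run at all.* This is true of the literal wording only. Once the instrument is corrected, baseline to 6 months has scheduled EPIC data at both ends, although the group definition is still needed for the between-group test.
- *The instrument would be picked after seeing the data.* Only EPIC is visibly collected, so there is no choice of instrument to exploit. The choice of domain can properly be left to a statistical analysis plan.
- *EPIC at the other times has no planned use.* The initial longitudinal analyses in section 7b are not limited to particular times; the 2- and 6-month restriction belongs to the additional analysis. Section 5.2 also gives EPIC a purpose, namely the outcome of treatment.
- *The QLQ-C30 will certainly never be given.* This is an inference from silence. The flow chart in section 5.1 is not in the text available. The inference is reasonable, because section 5.2 has an item devoted to the quality-of-life survey and it lists EPIC alone. The exact statement is that no visible procedure schedules the QLQ-C30.

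It can also be said that a 2-month clinic review already exists, so a survey could be added there. That is possible, but it would mean new data collection, whereas moving the analysis time would not.

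**Conclusion.** Section 7b is wrong as written and should be corrected. The instrument it analyses is not the one scheduled, and one of its two follow-up times has no survey. Neither planned change comparison has scheduled data as the text stands; substituting EPIC restores one of the two. The contrast between standard eLND and super-eLND is a further obstacle in the same paragraph, since the design has a single group and the second category is undefined.

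The conclusion assumes that the flow chart missing from the available text schedules no QLQ-C30 and no 2-month survey. It concerns a secondary outcome only. Sensitivity, specificity, concordance and the power calculation are not touched, so this is a should-fix internal inconsistency and not a threat to the trial's main conclusion.

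**What to change.** Amend section 7b in one edit:

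1. Replace EORTC QLQ-C30 with EPIC scores.
2. Replace the 2- and 6-month times with scheduled EPIC times, for example 3 and 6 months.
3. Reconcile the group contrast with section 3.2. Either define standard eLND and super-eLND from the recorded extent of dissection and call the comparison non-randomised and exploratory, or drop the contrast and analyse within-patient change from baseline. Under the second option the between-group tests must be replaced too. Whichever is chosen, make the complication-score comparison consistent with it.

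The cost is a wording change. It needs no new data collection, adds no burden for participants and leaves the primary analysis as it is. The general cancer questionnaire given up is one that no visible procedure collects. The price of the first option in step 3 is a weaker claim, because men with a wider dissection may differ from the others for reasons linked to their disease. The second option gives up any comparison by extent of surgery.
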